3.4.1 Sample size

At least forty (40) existing microfinance group clusters with n=900 people living with HIV (PLWH) will be randomized in a 1:1 ratio to either Study Arm A (MF+ICB) or Study Arm B (MF+SOC). Half of the cluters will be randomized to receive MF+ICB, resulting in approximately 450 PLWH in 20 groups in each of the MF+ICB and MF+SOC arms.

The number of participants enrolled in Study Arm C (SOC) will be 300 people living with HIV currently receiving care at an AMAPTH facility and not participating in group microfinance. As participants will not be randomized to the SOC arm, we will match SOC individuals to individuals in MF groups (in a 1:3 ratio) such that individuals have similar characteristics with respect to key individual and cluster-level variables.^{73,74} To match individuals, we will use covariates associated with both microfinance enrollment and viral suppression. We will use coarsened exact matching, and check statistical balance of preexposure covariates for an explicitly stated specification. Section 5.2 of this protocol (Enrollment of patients receiving facility-based care and not engaged in microfinance) details the steps that will be used to match and enroll 300 standard of care facility patients.

3.4.2 Power calculation

For the sample size calculations, the standard deviation of the group size was set to 5, type-one error rate to 0.05, a two-sided test, and the intra-class correlation coefficient to 0.05. Based on studies of the effect of financial interventions we expect at least 15% increase in viral suppression between MF+ICB and MF+SOC, between MF+SOC and SOC only, and between MF+ICB and SOC only groups. ^{13,45} The power calculations used viral suppression in MF+SOC ranging from 20 to 50% and, as in the BIGPIC trial, accounted for 15% dropout. ⁴³ For all the different scenarios considered, the power to detect a 15% increase in viral suppression was greater than 80% for testing all three hypotheses.

4. Aim 1 RCT Methods: Enrollment

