1.1 Background

Despite gains in antiretroviral therapy (ART) coverage for people living with HIV (PLHIV) and reductions in HIV-related morbidity and mortality, significant gaps remain: only 50% of PLHIV in sub-Saharan Africa are virally suppressed.¹ It is well known that retention in HIV care is a critical and necessary step in the continuum leading to viral suppression (VS). We have documented individual and system-level barriers to full engagement in care in western Kenya: distance to facilities, inefficient vertical care delivery, and limited means for transport and food.²⁻⁴ For PLHIV, microfinance (MF) and other income-generating activities can effectively improve ART adherence and viral suppression through strengthened food security and household economic conditions,⁵⁻⁷ while community-based ART delivery for PLHIV significantly reduces barriers related to distance and inefficient care delivery.^{8,9} Integrating HIV into primary care improves the efficiency of care delivery while addressing the growing burden of non-communicable disease (NCDs) among PLHIV.¹⁰ However, most Kenyans are uninsured and pay out of pocket for non-HIV-related healthcare, borrow from friends/family, or pay through harambee (Kiswahili for "pulling resources together").¹¹ What is still not known is how to alter care delivery to help support PLHIV to be continually engaged in care once they achieve relatively stable health initially afforded by ART.

Retention in HIV care within current care delivery models in SSA continues to be sub-optimal. ¹²⁻¹⁴ The primary barriers for retention in HIV care in western Kenya are distance to facilities, inefficient vertical care delivery, and limited means for transport and food. Access barriers are heightened in remote locations because travel is more difficult and transportation fees are prohibitively high relative to income. ¹⁵ Overcoming these barriers is critical for PLHIV as care interruption leads to gaps in ART and eventual unsuppressed viral load, allowing for disease progression and increased transmission, and increased risk of drug resistance. ¹⁶ Barriers to access and retention to care are interrelated, and require creative delivery models that address multilevel determinants, including economic and access issues.

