To evaluate the extent to which delivering integrated community-based care for HIV, diabetes and hypertension within microfinance groups affects hemoglobin A1C (HbA1c) level among people living with HIV (PLWH).	The secondary endpoint will be absolute mean change in hemoglobin A1C (HbA1c) level (mmol/mol) over the 18-month study period.	Mean change in HbA1c has shown to be associated with longer-term cardiovascular benefit, even when traditional control thresholds are not met.

 $^{^2}$ See the Addendum to the overall project protocol starting on page 100 for changes made to the primary endpoint.

OBJECTIVES	ENDPOINTS	JUSTIFICATION
Our working hypothesis is that A>B>C in terms of HbA1c level, where (A) represents		
microfinance groups receiving integrated community-based care, (B) represents		
microfinance groups receiving facility-based care, and (C) represents facility-based		
care without microfinance.		

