7.2 Statistical analysis ⁶

The primary analysis of interest is comparing viral suppression at 18 months between the MF+ICB (Study Arm A) and MF+SOC groups (Study Arm B). As a secondary hypothesis, we will test MF+ICB vs SOC alone and MF+SOC vs SOC alone. To test both the primary and the secondary hypotheses we will use a generalized mixed effects model.³³ For the primary outcome, the model we will use is

$$log(P(Y_{ij}=1|I_j,S_j,VB_{ij},c_j)) = \beta_0 + \beta_1 I_j + \beta_2 S_j + \beta_3 VB_{ij} + c_j$$

⁶ See the Addendum to the overall project protocol starting on page 100 for changes made to the statistical analysis plan.

where, Y_{ij} is viral suppression at 18 months for participant i in cluster j, I_j is the indicator if cluster j is randomized to the MF+ICB arm, S_j is an indicator if cluster j comes from the SOC individuals, VB_{ij} is the baseline viral load for participant i in cluster j, and c_j is the random effect associated with cluster j. The estimator β_1 estimates the difference between the MF+SOC and MF+ICB arms and positive values indicate higher viral suppression in the MF+ICB arm. To test the primary hypothesis we will perform a hypothesis test for H_0 : $\beta_1 = 0$. To test the secondary hypothesis we will perform a hypothesis test for H_0 : $\beta_2 = 0$ and H_0 : $\beta_1 - \beta_2 = 0$.

For the secondary outcomes, we will modify the above model to reflect that retention in care is a proportion and the absolute mean change in systolic blood pressure and HbA1c level are each a continuous outcome. Dropout from the study will be handled using inverse probability weighting.³⁴ The design, analysis, and interpretation of the results from the trial will follow the recommendations given by the CONSORT statement on cluster randomized trials.³⁵ All data will be de-identified prior to the analysis phase.

- 8. Aim 2: Mixed methods to assess mechanisms through which MF and community-based care affect patient outcomes
- 8.1 Study Population and recruitment

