and capital (e.g., fuel) resources needed to travel to the distinct health facilities to ascertain secondary outcome data for each matched patient were prohibitively high.

- 8. In order to enroll 300 patients receiving standard facility-based care and not engaged in a microfinance group (SOC), the original protocol stated that enrolled microfinance group participants should be matched 3:1 to eligible SOC patients on county, gender, age (+/- 5 years), and health facility. The matching protocol was revised on February 8, 2022 such enrolled microfinance group participants were matched 3:1 to eligible SOC patients on gender and age (+/- 5 years of microfinance participant). This change was made because most SOC patients who were invited to enroll in Busia County after February 8, 2022 were ineligible for study participation due to membership in either a microfinance group or a community ART Group. This change resulted in approximately 90 enrolled microfinance group members in Busia County being matched to 30 SOC patients in Trans Nzoia County on (1) age (within +/- 5 years of the GISHE participant's age) and (2) gender.
- 9. The original project protocol stated that group randomization would occur using a computer-generated sequence to randomize microfinance groups to receive either integrated community-based care (ICB) or standard of care, and that the randomization process would be conducted centrally by biostatisticians at Brown University.

The cluster randomization approach was revised to use a transparent, community-engaged approach to increase transparency and cultivate trust between research personnel and study participants, clinical personnel, and local community leaders. Below is a summary of the steps that were implemented for at each community-engaged randomization ceremony. Six randomization ceremonies were conducted among the 57 microfinance groups following enrollment:

- 2 randomization ceremonies each with 10 microfinance groups were conducted in Phase I groups
- 2 randomization ceremonies each with 11 and 8 microfinance groups were conducted in Phase II groups
- 1 randomization ceremony with 15 microfinance groups was conducted in Phase III groups
- 1 randomization ceremony with 3 microfinance groups was conducted in Phase IV groups

The below steps describe the community-engaged randomization process.

Participants

- 1. Group leaders (Chairperson, Secretary & Treasurer)
- 2. AMPATHPlus Senior Technical Officers (STO)

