The original analysis plan used a generalized linear model as the primary analysis method. The change in the analysis plan was made without looking at within arm data, but was made after the high rate of viral suppression was known (i.e., overall outcome prevalence was known but no between arm comparisons had been done). The reason for the change was: We have partially clustered data as the individuals in Arms MF+ICB and MF+UC are in clusters while participants in the UC arm are not. The mixed effects model requires correct specification of the distribution assumptions of random effects while the GEE does not. As verifying the distribution assumptions on people in a single cluster is impossible, we thought a GEE would provide a better approach. A recent manuscript compared methods for analyzing partially clustered data and concluded "Analysis of partially clustered trials using GEEs with an independence working correlation structure may be preferred to avoid the limitations of mixed models and exchangeable GEEs" further supporting the change (this was published after the decision was made to change the analysis method).

⁸ Prague M, Wang R, Stephens A, Tchetgen Tchetgen E, DeGruttola V. Accounting for interactions and complex inter-subject dependency in estimating treatment effect in cluster-randomized trials with missing outcomes. Biometrics. Published online 2016. doi:10.1111/biom.12519

⁹ Lange, K. M., Sullivan, T. R., Kasza, J., & Yelland, L. N. (2024). Performance of mixed effects models and generalized estimating equations for continuous outcomes in partially clustered trials including both independent and paired data. Statistics in Medicine.

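### Does the power statement in section 3.4.2 fail because the trial later saw a high rate of viral suppression?

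*Combined protocol and SAP*

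**What the plan says.** Section 3.4.2 is the only power statement for the primary comparison. It sets a two-sided 5% type I error rate, an intra-class correlation of 0.05, a group-size standard deviation of 5 and 15% dropout, and says: "The power calculations used viral suppression in MF+SOC ranging from 20 to 50" per cent. It concludes that "the power to detect a 15% increase in viral suppression was greater than 80% for testing all three hypotheses". Section 3.4.1 supplies at least 40 groups and 900 participants for arms A (MF+ICB) and B (MF+SOC), and 300 for arm C. The only suppression figure elsewhere is in section 1.1: "only 50% of PLHIV in sub-Saharan Africa are virally suppressed".

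Addendum item 10 replaces the mixed model by a generalized estimating equation. It says that this change "was made after the high rate of viral suppression was known", and explains that "overall outcome prevalence was known but no between arm comparisons had been done". It gives no number.

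Footnotes in the body send the reader to the addendum for amended topics, for example "See the Addendum to the overall project protocol starting on page 100 for changes made to the primary endpoint" and "See the Addendum to the overall project protocol starting on page 100 for changes made to the statistical analysis plan". Section 3.4.2 carries no such footnote, and none of the 11 addendum items mentions power. Item 9 does record a larger number of clusters: "Six randomization ceremonies were conducted among the 57 microfinance groups following enrollment".

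**The concern.** If suppression in arm B is 20-50% and arm A gains exactly 15 points, the pooled rate in equal arms A and B lies between (20 + 35)/2 = 27.5% and (50 + 65)/2 = 57.5%. A rate that the investigators call high hardly fits that range. Participants had to be in HIV care and on ART for at least six months, so a rate well above 50% is plausible.

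The worry is how a null primary result would be read. A reader might credit the trial with more than 80% power for a 15-point gain at a base rate that it did not have. Above 85% in arm B, that gain is arithmetically impossible, and the gains that remain possible could be underpowered. Six other topics were cross-referenced to the addendum, so the silence here looks like an oversight.

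**Working it through.** **Inputs.** Sections 3.4.1 and 3.4.2: 40 groups, 900 enrolled (450 per arm), mean group size 900/40 = 22.5, SD 5, ICC 0.05, dropout 15%, two-sided alpha 0.05. Arm B rates above 50% are assumptions, because the documents give none.

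**Effective sample size.** DE = 1 + ((1 + CV²)m − 1) × ICC, with CV = 5/22.5 = 0.222, so 1 + CV² = 1.049. Completers per arm: 450 × 0.85 = 382.5.

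- m = 22.5 × 0.85 = 19.1 (group size after dropout): DE = 1.95, effective n = 382.5/1.953 = 195.8 per arm.
- m = 22.5 (group size before dropout): DE = 2.13, effective n = 382.5/2.131 = 179.5 per arm.

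**Power.** Φ(d/SE − 1.96), where SE² = [p_A(1 − p_A) + p_B(1 − p_B)]/n_eff and d = p_A − p_B. The opposite tail is negligible except in the relative reading, where it is included.

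**The plan's own figure, A versus B, +15 points**

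| Arm B rate | n_eff 195.8 | n_eff 179.5 |
|---|---|---|
| 20% | 92.1% | 89.8% |
| 42.5% (minimum) | 85.1% | 82.0% |
| 50% | 85.9% | 82.9% |

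A pooled-variance test with a t reference on 38 degrees of freedom gives 80.1% at its lowest. The stated figure therefore reproduces. A relative increase of 15% gives only 11% at 20% (20% against 23%) and 30-32% at 50% (50% against 57.5%). Only percentage points agree with the text, so the intended meaning can be recovered.

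**The other two hypotheses.** Take arm C as unclustered, as addendum item 10 describes it, with 300 × 0.85 = 255 completers. B versus C then has 89% power (50% against 35%) to 99.8% (20% against 5%). A versus C with a 15-point gap has 89-94% for arm C rates of 20-50%. If arm C were treated as clustered, B versus C would fall to 76% at 50% against 35%, but that is not the design.

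**Arm B rates above the planned range, +15 points**

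| Arm B rate | n_eff 195.8 | n_eff 179.5 |
|---|---|---|
| 60% | 89.4% | 86.7% |
| 70% | 95.1% | 93.3% |
| 80% | 99.6% | 99.3% |

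Power rises because p(1 − p) shrinks as both rates move away from 50%. A Wald test on the log odds ratio, closer to the revised analysis, gives much the same: 85% at 50%, 94% at 70% and 99% at 80%. At 85% the gain needs full suppression in arm A. Above that it cannot happen.

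**Smaller gains, which section 3.4.2 does not address**

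- 85% against 95%: 89-92%.
- 90% against 98%: 90-92%.
- 85% against 92.5% (non-suppression halved): 62-66%.
- 90% against 95% (non-suppression halved): 44-47%.

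With 57 groups and an assumed 900 enrolled, the last two become 69-72% and 50-53%.

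**What the high rate proves.** If arm B were at its planned ceiling of 50% and arm A at 100%, the pooled rate would be (50 + 100)/2 = 75%. Section 3.4.2 expects a gain of at least 15, so only a pooled A and B rate above 75% would rule out an arm B rate inside the planned range. The addendum gives no number, and its overall prevalence may include arm C.

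**What the addendum is for.** Its opening sentence limits it to changes made to the protocol after data collection began. The footnotes likewise point to changes. The power calculation was not changed.

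**The case for a change.** The best case for a note is that section 3.4.2 was never superseded, so it still stands as the trial's account of its power. The investigators held the pooled rate and could have added one footnote and one calculation without touching the analysis. A minimum detectable difference based on the pooled rate would also avoid the circularity of power computed from the observed effect. With 57 groups, an assumed 900 enrolled and ICC 0.05, it would be about 10.4-10.8 points at a pooled 80%, 7.8-8.1 at 90% and 5.7-5.9 at 95%.

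Much of this stands. The rate probably did exceed the planned range, and the wording of the 15% is loose. It does not follow that the plan needs changing. A planning assumption overtaken by data is not in conflict with those data. A text that says the assumption was not met would assert more than the documents show. A null result will be read from the 95% confidence interval specified in addendum item 10, which reflects the achieved clusters, numbers and prevalence directly. A detectable difference calculated after the analysis would add little to it. The pooled rate is a result and belongs in the results report.

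**Conclusion.** The concern does not hold as a defect of the plan. The figure of more than 80% is correct on its own inputs (82-92% for A versus B) and remains true for a 15-point gain at every arm B rate up to 85%. Beyond that, the gain is unattainable rather than underpowered. Low power, such as 44-47% for 90% against 95%, needs two things that the documents do not establish: a very high arm B rate and interest in an effect smaller than the one planned for.

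What is left is an optional remark for the results paper, together with a loose use of 15% that the arithmetic resolves as percentage points. Neither would alter the estimand, the test, the analysis set or a conclusion.

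This rests on the plan's ICC of 0.05 still applying at high prevalence, on 900 participants being enrolled, and on arm C being unclustered.

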4.1 Enrollment of microfinance group members

After identifying eligible microfinance group members, project personnel will use Adult Consent Form I (Appendix I) to obtain written informed consent from eligible GISHE group members (who will later be randomized to Study Arm A or to Study Arm B). For eligible GISHE group participants, informed consent will be collected in-person during a regularly scheduled GISHE group meeting.

Among microfinance group members, the Aim 1 enrollment period will begin on November 1, 2020 and end when the enrollment target of n=900 GISHE group members has been met. Obtainment of written informed consent will be recorded in REDCap.

General Steps for Obtaining Written Informed Consent

- The informed consent process should always occur in a private, confidential, and safe location.
- Elaborate on the objectives and purposes of the study and why the potential participant may qualify. Review the procedures that will be required of the participant. This includes naming the procedures, the time duration of the study, and location of where it will take place. Describe all of the risks and benefits for the procedures that are involved. Ensure that the potential participant has sufficient time to ask questions.
- If the subject is willing to participate under his or her own free will or the subject's legally authorized representative (LAR) agrees to the subject's participation, informed consent should be documented in the following ways:

- a. The subject or the subject's legal representative signs, personally dates and prints his or her name in block letters on the consent form; and
- b. The person who conducts the informed consent process signs, personally dates and prints his or her name in block letters on the consent form.
- Provide a paper copy of the signed and dated ICF to the subject and/or the subject's LAR.
- Store all signed informed consent forms securely in compliance with local IRB approvals and following the study's Aim 1 Data Management Protocol.

4.2 Enrollment of patients receiving facility-based care and not engaged in microfinance ³

Among AMPATH patients not participating in group microfinance, the Aim 1 enrollment period will begin on August 1, 2021 and end when the enrollment target of n=300 standard care patients has been met. Obtainment of written informed consent will be recorded in REDCap. The following steps specify the process that will be used for matching and enrolling 300 standard of care patients.

Step 1. Using AMPATH's Medical Record Systems (AMRS), the project's data manager will filter all patient records in AMRS so that only those SOC patients who meet the following eligibility criteria are selected:

- Age: 18 years of age or older
- County of residence: Busia or Trans Nzoia
- County where patient receives care: Busia or Trans Nzoia
- HIV Status: currently living with HIV
- ART Status: Has been taking ART medications for ≥ 6 months
- Pregnancy Status: Not currently pregnant at most recent HIV care visit
- CARG Status: Not a member of a community ART group (CARG)

Filtering all AMRS patients by eligibility criteria will create a master list (**List 1**) of AMRS patients who can be matched to enrolled microfinance group members. List 1 will need to contain at least 1200 patients (300 SOC patients with 4 potential backups).

Step 2. Each time a group of GISHE participants are newly enrolled in Study Arm A or B (e.g., monthly or quarterly), the study's Data Assistant will send a list of the newly enrolled GISHE group members to the Data Manager so that the Data Manager can match these GISHE participants 3:1 to eligible SOC patients from List 1. The list of newly enrolled GISHE group members will contain, at minimum, the following information:

- Harambee Study ID
- AMRS ID (if available)
- CCC Number (if available)
- Universal ID (if available)
- County of Residence (Busia or Trans Nzoia)
- Age
- Gender

³ See the Addendum to the overall project protocol starting on page 100 for changes made to the standard of care matching process.

• Name of health facility where patient receives routine HIV care

The Data Manager should match SOC patients from List 1 to enrolled GISHE group members on:

- (1) County of Residence,
- (2) Age (within +/- 5 years of the GISHE participant's age),
- (3) Gender, and
- (4) Health Facility

The Data Manager should also match the originally matched SOC patient to 4 backup SOC patients who have the same county, gender, age, and health facility as the original SOC patient. If exact matching for the original SOC patient is not possible, county and gender should be identical for all 4 ordered backups and then select each backup SOC patient whose age is closest to the original SOC patient. **List 2** should contain, at minimum, the following information:

- Harambee Study ID of matched GISHE participant
- Age, sex, county, and health facility of matched GISHE participant
- AMRS ID of 5 matched SOC patients (1 originally matched SOC patient and 4 ordered backups)
- CCC Number of the 5 matched SOC patients (if available)
- Universal ID of the 5 matched SOC patients (if available)
- Age, sex, county, and health facility of all 5 matched SOC patients

The Data Manager should return List 2 to the Data Assistant. In addition to the Harambee Study IDs, AMRS IDs, and other relevant IDs (e.g., CCC Number), List 2 should be formatted as in below example screen shot that contains faux data:

	Α	В	С	D	E	F	G
1	id	case	idmatch	age	county1	sex	facility
2	1	1	1	32	1	0	Teso
3	1278	0	1_1	32	1	0	Teso
4	3336	0	1_2	32	1	0	Teso
5	3433	0	1_3	32	1	0	Teso
6	3609	0	1_4	32	1	0	Teso
7	4189	0	1_5	32	1	0	Teso
8	2	1	2	59	1	1	Port Victoria
9	763	0	2_1	59	1	1	Port Victoria
10	996	0	2_2	59	1	1	Port Victoria
11	1408	0	2_3	59	1	1	Port Victoria
12	1520	0	2_4	59	1	1	Port Victoria
13	2031	0	2_5	59	1	1	Port Victoria
14	3	1	3	22	1	0	Khunyangu
15	905	0	3_1	22	1	0	Khunyangu
16	2023	0	3_2	22	1	0	Khunyangu
17	4176	0	3_3	22	1	0	Khunyangu
18	6207	0	3_4	22	1	0	Khunyangu
19	6541	0	3_5	22	1	0	Khunyangu

In the example screenshot: id = deidentified dummy ID; case = 1(GISHE participant) / 0(SOC Patient); sex = 1 (male) / 0 (female); county1 = 1(Busia) / 0(Trans Nzoia); facility = name of health facility where patient receives HIV care. The idmatch variable indicates the

GISHE participant (e.g., idmatch = 1) and the 5 SOC of patients to whom they were matched (e.g., idmatch = 1 1, 1 2, 1 3, 1 4, 1 5).

Step 3. Working closely with the AMPATH Retention Team, Harambee Data Assistant will use the AMRS ID from the list of matched SOC patients (**List 2**) to retrieve a given patient's contact information from their AMPATH medical record.

Step 4. In both Trans Nzoia and Busia counties, the AMPATH Retention Team will then call each matched SOC patient on List 2 and introduce them to the Harambee RA who will - invite them to enroll in Study Arm C. If there is no phone number available for the first identified SOC patient in AMRS (e.g., idmatch = 1_1 for GISHE Participant with idmatch = 1), then the RA will visit the facility that the client belongs to and obtain the contact information available. If a phone number is still not identifiable, then the team member should proceed with contacting the next matched SOC patient for that GISHE participant (e.g., idmatch = 1_2 for GISHE participant with idmatch = 1).

Step 5. To maximize efficiency, each original SOC patient and each backup SOC patient on List 2 should be contacted no more than twice to be invited to enroll in Aim 1. If a SOC patient is not able to be reached on the second attempt, the AMPATH Outreach Team of Harambee Data Assistant should proceed with contacting the next relevant patient on List 2. SOC patients who are unable to be reached after 2 attempts should not be contacted at a future date to be invited to enroll. Because a total of n=900 GISHE participants and total of n=300 SOC patients will be enrolled during Aim 1 (GISH Participants matched 3:1 to SOC patients), only one-third of matched SOC patients from List 2 list should be enrolled.

Step 6. For SOC patients who indicate that they are interested in enrolling in Aim 1, Harambee RA will first confirm eligibility over the phone and then schedule a time to complete informed consent procedures in-person using Adult Consent Form II (Appendix II). RA will complete in-person informed consent at a mutually convenient location agreed upon by the RA and the SOC patient (e.g., at an AMPATH-supported health facility during the patient's regularly scheduled HIV care visit).

